### **Secondary Outcomes**

Eye tracking secondary outcomes: 1) number of times looking at the FOP sodium label (i.e., fixation count), 2) time to first fixation on the FOP sodium label, and 3) dwell time on “natural” claim.

*Hypothesis 2.* We predict that each of the three intervention FOP sodium label types will elicit higher levels of the 3 secondary eye-tracking outcomes (fixation count on the FOP sodium label, self-reported attention to the FOP sodium label, and perceived message effectiveness of the FOP sodium label), compared to the control. We predict that the pictorial FOP sodium label will elicit higher amounts of these outcomes than the icon label, the icon label will elicit higher amounts than the text-only label, and the pictorial label will elicit higher amounts than the text-only label.

Other secondary outcomes: 1) self-reported attention to the FOP sodium label, assessed with 1 item for each label type adapted from Nonnemaker et al. 2010, 2) perceived message effectiveness of the FOP sodium label, assessed with 3 items for each label type, adapted from Baig et al. 2019, and 3) how understandable the FOP sodium label was, assessed with 1 item for each label type, adapted from Brewer et al. 2019. Response options for all measures will range from 1 (low values) to 5 (high values).

*Hypothesis 3.* We predict that each of the three intervention FOP sodium label types will elicit lower levels of two outcomes (time to first fixation on the FOP sodium label and dwell time on the “natural” claim), compared to the control. We predict that the pictorial FOP sodium label will elicit lower amounts of these outcomes than the icon label, the icon label will elicit lower amounts than the text-only label, and the pictorial label will elicit lower amounts than the text-only label.

### **Statistical Methods**

We will assess the impact of FOP sodium label type on the primary and secondary outcomes using mixed effects linear regression models to account for repeated measures. We will use separate models for each outcome.

#### 1. Analyses of the primary outcome:

- a. We will run a mixed effects linear regression model, regressing dwell time on an indicator variable for FOP sodium label type. The control label will be the reference group. The model will treat the intercept as random. We will use pairwise comparisons to compare predicted means for the three intervention FOP sodium label types to each other.

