## **Study Protocol**

Participants will complete a randomized experiment programmed using Tobii Lab Pro software and Qualtrics. After providing informed consent, participants will view images of cans of soup with 4 different labels (a text-only sodium label, an icon and text sodium label, a pictorial and text sodium label, and a control barcode label). Participants will view each label in a random order. An eye tracker will be used to measure amount of time spent looking at the front-of-package sodium label (i.e., dwell time) (primary outcome) and secondary outcomes: number of times looking at the front-of-package sodium label (i.e., fixation count), time to first fixation on the front-of-package sodium label, and dwell time on “Natural” claim. After viewing all labels, participants will use Qualtrics to rate each label for the remainder of secondary outcomes: self-reported attention to front-of-package sodium label, perceived message effectiveness of front-of-package sodium label, and understandability of front-of-package sodium label.

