### **Primary Outcome**

Primary outcome: Amount of time spent looking at the FOP sodium label (i.e., dwell time). This outcome will be measured using eye tracking technology.

*Hypothesis 1.* We predict that each of the three intervention FOP sodium label types will elicit higher dwell time on the FOP sodium label compared to the control. We predict that the pictorial FOP sodium label will elicit higher amounts of dwell time than the icon label, the icon label will elicit higher amounts than the text-only label, and the pictorial label will elicit higher amounts than the text-only label.

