#### 2. Analyses of the secondary outcomes:

- a. We will use the same modeling approach used in the primary outcome to examine the impact of FOP sodium label type on secondary outcomes.

For analyses of primary and secondary outcomes, we will use the Benjamini-Hochberg method to correct for multiple tests. These analyses will treat each outcome as a family of tests, correcting for the six tests within each outcome and controlling the false discovery rate at 0.05.

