### **Sample Size Needs**

Respondents will be approximately 60 US adults ages 18+ who identify as Latino. We powered the study to detect an effect size of  $d=0.27$  or larger, assuming 4 repeated measures, 80% power, a correlation among repeated measures of 0.60, and a nonsphericity correction of 1. This effect size is conservative given that our recent meta-analysis found a large effect size for the impact of pictorial (vs. text) warnings on dwell time ( $d=1.74$ ) in eye tracking studies.

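### The eye-tracking models leave out viewing position although the four labels are seen in random order: valid, but less precise if position explains more than about 2% of within-person variance

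*Combined protocol and SAP*

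**What the plan says.** Under Study Protocol, every participant sees soup cans carrying four labels (text-only, icon, pictorial and a control barcode) while an eye tracker records: "Participants will view each label in a random order". No counterbalancing is described.

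Under Analyses of the primary outcome, the model is: "We will run a mixed effects linear regression model, regressing dwell time on an indicator variable for FOP sodium label type". The control is the reference, and "The model will treat the intercept as random". Under Analyses of the secondary outcomes: "We will use the same modeling approach used in the primary outcome". Each outcome is one Benjamini-Hochberg family, "correcting for the six tests within each outcome and controlling the false discovery rate at 0.05".

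Viewing position, period or order appears in no model in the synopsis or under Statistical Methods, and no sensitivity analysis for order is described.

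**The concern.** Looking behaviour may change between the first and the fourth image, through novelty or fatigue. Because order is random, such a change does not bias label comparisons on average. Without a position term, however, it remains in the within-person residual and widens the intervals for all six contrasts.

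What is at stake is precision for the small contrasts. The reassuring effect size under Sample Size Needs, d=1.74, is described as "a large effect size for the impact of pictorial (vs. text) warnings on dwell time". It says nothing about the finer ordering that Hypothesis 1 also predicts, for example that "the icon label will elicit higher amounts than the text-only label". The documents give no expected size for that step.

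The point concerns the four eye-tracking outcomes only. The survey ratings are collected after all labels have been viewed.

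**Working it through.** **Inputs from Sample Size Needs and General Principles.** About 60 participants, 4 repeated measures, d=0.27, 80% power, "a correlation among repeated measures of 0.60", nonsphericity correction 1, two-sided alpha 0.05.

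**Assumptions.** Total SD 1, one viewing per label, unrestricted random order, additive position effect with a linear decline. The share q of within-person variance due to position is not in the documents and is varied.

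**1. The plan's own figure.** The documents do not name the test behind d=0.27. A repeated-measures F test with f = d/2 reproduces it:

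- f = 0.27/2 = 0.135; within-person variance = 1 − 0.60 = 0.40
- λ = f² × 60 × 4 / 0.40 = 0.018225 × 240 / 0.40 = 10.935
- df = 3 and 3 × (60 − 1) = 177
- power = 79.2%, against the stated 80%.

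**2. Validity without the term.** In simulation with no label effect, type I error per contrast was 0.049 to 0.051 and bias at most 0.0015. A second simulation, with position effects from none to strong (a linear trend or a first-view effect), gave type I error 0.044 to 0.055 and bias at most 0.004.

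**3. Cost of the term.** Position as a four-level factor takes 3 df (177 to 174). Under unrestricted order the label-contrast variance rises on average by 177/174 = 1.0172, so the SE rises by √1.0172 = 1.0086, about 0.9%. Over 4,000 simulated sets of 60 random orders the mean factor was 1.0173 (95% of sets between 1.005 and 1.037).

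**4. Break-even.** The variance ratio with versus without the term is (1 − q) × 1.0172. It equals 1 at q = 1 − 1/1.0172 = 1.69%. A linear decline D over four positions adds (5/27)D² = 0.1852D² to within-person variance, so q = 1.69% means D = √(0.0169 × 0.40 / 0.1852) = 0.19 SD. Shares of 5% and 10% correspond to 0.33 and 0.46 SD.

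**5. Power if 0.60 is the raw correlation (position already inside it).** The two power columns use different effect patterns and must not be read together. The F-test column is the sample-size calculation of step 1 with λ = 10.935 / [(1 − q) × 1.0172] and df 3 and 174; without the term it stays at 79.2%. The last column simulates the six planned pairwise tests with Benjamini-Hochberg at 0.05 (20,000 trials per case), labels equally spaced 0.27 apart, mean of the three adjacent steps.

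| Position share q | F test, with term | Adjacent step, without / with term |
|---|---|---|
| 0% | 78.4% | 62.2% / 61.4% |
| 2% | 79.3% | 62.3% / 62.6% |
| 5% | 80.6% | 62.2% / 64.0% |
| 10% | 82.9% | 62.5% / 66.5% |

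Monte Carlo error for a single contrast is about √(0.62 × 0.38 / 20,000) = 0.3 points. At steps of 0.5, adjacent-step power is about 99% with or without the term.

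**6. Power if 0.60 excludes position.** A 0.5 SD decline adds 0.1852 × 0.25 = 0.0463 to 0.40, an inflation of 1.116. The F-test figure falls to 74.1% without the term and is 78.4% with it. Adjacent-step power is 57.3% without and 61.6% with it.

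**7. In participants.** To match the adjusted model with 60 people, the planned model would need 60/0.9664 = 62 at a 5% share and 60/0.9156 = 66 at 10%.

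**The case against.** The strongest objection is that nothing is wrong. Label type plus a random intercept is a legitimate model for a randomised within-person experiment, and a position covariate is a matter of preference. Even the sign of the net effect is unknown: below a share of about 2% the term costs a little precision, and no passage supports 5% or 10%. If 0.60 is the raw correlation, nothing is lost against the plan's own power target. All of this stands, and it is why the point is an optional improvement.

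Three further objections limit how the figures may be used. First, the SAP plans six pairwise tests and no omnibus test, so the F-test figures describe only the sample-size calculation. They also rest on a smaller spread (f = 0.135) than labels 0.27 apart, which give f = 0.27 × √1.25 = 0.302. Second, the break-even assumes unrestricted orders; with balanced orders it would be near zero, which favours the term. Third, all calculations use one generic normal outcome; nothing is specific to fixation count, time to first fixation or dwell time on the natural claim.

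None of these removes the point. The expected cost is under one power point, and the possible gain is several times larger.

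**Conclusion.** The point holds as a low-cost, optional improvement. The planned analysis is valid for additive position effects and may be kept. With 60 participants and unrestricted order, it is less precise than the data allow once position explains more than about 1.7% of within-person variance. At a 5% share the gain is about 1.8 power points for an adjacent step of d=0.27 (64.0 − 62.2); at 10% it is about 4 points (66.5 − 62.5). Below the break-even there is no gain, and for contrasts of about d=0.5 or more it is negligible. The position share, the linear decline and the equal steps of 0.27 are assumptions that the documents neither support nor exclude. Carryover from one label to the next is a separate matter, which a position term would not resolve.

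**What to change.** Pre-specify viewing position (1 to 4, categorical) as a fixed effect in the mixed models for dwell time on the label, fixation count, time to first fixation and dwell time on the natural claim. Carry the presentation order, which the experiment already generates, into the analysis file. Label contrasts, the Benjamini-Hochberg rule, the survey models, sample size and procedures stay as they are.

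The cost is one model term and 3 of 177 residual df. If position has no effect, the SE is about 0.9% larger and adjacent-step power at d=0.27 goes from 62.2% to 61.4%. The choice should be fixed before the data are seen, because a covariate added afterwards would be discretionary. It would also help to state whether presentation orders are unrestricted or balanced, since balance makes the term almost free.

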#### 2. Analyses of the secondary outcomes:

- a. We will use the same modeling approach used in the primary outcome to examine the impact of FOP sodium label type on secondary outcomes.

For analyses of primary and secondary outcomes, we will use the Benjamini-Hochberg method to correct for multiple tests. These analyses will treat each outcome as a family of tests, correcting for the six tests within each outcome and controlling the false discovery rate at 0.05.

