## **Protocol Synopsis**

Study Title	Visual Attention to Text and Pictorial Food Labels: An Eye Tracking Experiment
Funder	National Heart, Lung, and Blood Institute (NHLBI)
Clinical Phase	NA
Study Rationale	

• Adults in the US consume excessive sodium, added sugars, and saturated fats, leading to high rates of hypertension, type 2 diabetes, and heart disease.

• Structural factors like targeted marketing of unhealthy foods, price barriers, and low use of Nutrition Facts labels contribute to worse dietary outcomes among Latino populations.

• Front-of-package (FOP) food labels, especially "high-in" labels (e.g., "High in sugar"), are a promising policy solution to reduce purchase of unhealthy foods.

• Visual elements like icons and graphics in FOP labels may be more effective for Latino and limited English proficiency populations by improving noticeability and comprehension.

• However, it's unknown how different types of FOP labels affect visual attention, message effectiveness, and understandability among Latino and limited English proficiency populations.

Study Objective(s)	The primary objective of this study is to examine attention elicited by different types of FOP sodium labels (i.e., FOP sodium label types) among adults identifying as Hispanic or Latino/a/é (hereinafter Latino).  Primary 

• To evaluate whether intervention FOP sodium labels elicit higher dwell time on the FOP sodium label than control messages.

 Secondary 

• To evaluate whether intervention FOP sodium labels elicit higher levels of 3 secondary outcomes (fixation count on the FOP sodium label, self-reported attention to the FOP sodium label, and perceived message effectiveness of the FOP sodium label), compared to the control.

• To evaluate whether (1) self-reported attention to the FOP sodium label, (2) perceived message effectiveness of the FOP sodium label, and (3) how understandable the FOP sodium label was differs by label type.

Study Design	Within-participants randomized experiment.
Subject Population key criteria for and Exclusion:	
Inclusion Criteria
 

1. Age 18 and older

2. Self-identifies as Hispanic or Latino

 
Exclusion Criteria

---

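### For understandability, does the plan leave open whether the barcode control is compared, and so whether three or six tests are corrected for?

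*Combined protocol and SAP*

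**What the plan says.** Understandability is one of seven outcomes. Under Secondary Outcomes it is listed as "how understandable the FOP sodium label was, assessed with 1 item for each label type", on a 1 to 5 scale.

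The Synopsis has two secondary objectives. The first concerns the control and names what is to be tested against it: "higher levels of 3 secondary outcomes (fixation count on the FOP sodium label, self-reported attention to the FOP sodium label, and perceived message effectiveness"; understandability is not in that list. The second takes self-reported attention, message effectiveness and understandability, and ends by asking whether "how understandable the FOP sodium label was differs by label type".

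Hypothesis 1 covers dwell time. Hypothesis 2 covers the same three outcomes as the first objective. Hypothesis 3 predicts that each of the sodium labels "will elicit lower levels of two outcomes (time to first fixation on the FOP sodium label"; the other of its two outcomes is natural-claim dwell time. Understandability has no hypothesis.

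Statistical Methods, item 1, sets up the model: "The control label will be the reference group", with the three sodium labels then compared pairwise. Item 2 uses the same approach for the secondary outcomes and closes by "correcting for the six tests within each outcome and controlling the false discovery rate at 0.05". The Study Protocol section says that after viewing all four labels "participants will use Qualtrics to rate each label for the remainder of secondary outcomes".

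**The concern.** Self-reported attention and message effectiveness appear in both secondary objectives. That suggests two separate questions, one against the control and one among the sodium labels, with understandability belonging only to the second. It is also the only outcome without a prediction of any kind. On that reading its family would hold three tests, while the analysis section counts six.

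The count matters because Benjamini-Hochberg cut-offs depend on it, and the effect can go either way. If the barcode is rated clearly worse than the sodium labels, its three small p-values ease the cut-offs for the label pairs. If it is rated about the same, its three large p-values tighten them. An analyst free to choose after seeing the ratings could pick the more favourable family. Label comprehension in Latino and limited-English populations is part of the stated rationale, so the outcome is not trivial.

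**Working it through.** **The plan's own figure.** There are four labels: text-only, icon, pictorial and barcode control (Study Protocol). With the control as reference there are 3 contrasts against control. Pairwise comparison of three sodium labels gives 3 × 2 / 2 = 3 more. Total 3 + 3 = 6, which equals 4 × 3 / 2. The stated six is reproduced, and only if the control contrasts are included. Leaving the control out gives 3.

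**Outcomes covered by hypotheses.** Hypotheses 1, 2 and 3 cover 1 + 3 + 2 = 6 of the 7 outcomes. The one left out is understandability.

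**Do the objectives list the contrasts to be run?** Set beside the rest of the plan, they do not:

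- Fixation count is absent from the objective on differences by label type, yet Hypothesis 2 ranks the three sodium labels on it.
- The primary objective mentions only the control, yet Hypothesis 1 and item 1 of Statistical Methods compare the sodium labels with each other.
- Time to first fixation and dwell time on the natural claim are in no objective, yet Hypothesis 3 gives them both kinds of contrast.

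If omission from a bullet removed a contrast, these outcomes would lose contrasts that the plan plainly intends. The omission of understandability from the first bullet therefore carries little weight. Nor does a difference by label type exclude the control, because the model makes the control one level of the label-type variable.

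**What the count would change.** Cut-off for rank i of m tests: 0.05 × i / m.

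- m = 6: 0.0083, 0.0167, 0.0250, 0.0333, 0.0417, 0.0500
- m = 3: 0.0167, 0.0333, 0.0500

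Example A: label-pair p-values 0.03, 0.20, 0.60. With m = 3 nothing is declared (0.03 > 0.0167, 0.20 > 0.0333, 0.60 > 0.05). With m = 6 and all control p-values below 0.001, 0.03 ranks fourth and 0.03 ≤ 0.0333, so one label pair is declared.

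Example B: label-pair p-values 0.012, 0.20, 0.60. With m = 3, 0.012 ≤ 0.0167 gives one finding. With m = 6 and control p-values 0.3, 0.4, 0.5, 0.012 > 0.0083 and no later rank passes, so there is none.

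**How often.** A simulation used N = 60 and correlation 0.60 (Sample Size Needs), with 40,000 trials per scenario. A latent normal was cut at −1.6, −0.9, −0.2 and 0.6 to give a 1 to 5 item. The six-test analysis uses all four labels (59 × 3 = 177 error df); the three-test analysis uses the sodium labels only (59 × 2 = 118). The cut points, control gaps and label differences are assumptions, since the plan gives no effect size for this outcome.

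| Scenario | At least one label-pair verdict differs | Any label-pair finding, six vs three tests |
|---|---|---|
| Pictorial 0.27 SD above the other two labels, control 1 SD lower | 11.8% | 60% vs 52% |
| Pictorial 0.27 SD above the other two labels, control equal to text | 13.4% | 44% vs 51% |
| Eight scenarios with a true label difference | 11.0% to 16.6% | |
| Sodium labels equal | 2.4% to 3.2% | |

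These figures combine two departures from the plan: a smaller family, and removal of the control from the model. With the family held at three tests, the model change alone alters at least one label-pair verdict in about 6% of simulated trials.

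**The case for a change.** The strongest case for a change is that a general sentence about all outcomes does not obviously override an objective specific to one of them. Repeating two outcomes across the two bullets is pointless unless the bullets ask different questions. The Synopsis, which also describes the correction, gives no test count that would settle the matter. The remedy would be one sentence, and neither family size is uniformly the more conservative.

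Part of this stands. No objective or hypothesis states a comparison of understandability with the control, although the analysis section implies one, and the two texts could be better aligned. The Benjamini-Hochberg examples are correct too.

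The inference that three tests are equally defensible does not stand. It would set aside an explicit number in the analysis section on the strength of an omission from a list that is incomplete for several other outcomes, all of which are accepted at six tests. The missing hypothesis does not help it: General Principles makes every test two-sided, so a contrast needs no predicted direction to be run or counted.

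**Conclusion.** No change to the plan follows. Statistical Methods fixes the analysis of understandability: four labels, control as reference, six two-sided tests, false discovery rate 0.05 within the outcome. An analyst who follows the text has one route, and it is sound. The 11.0% to 16.6% disagreement rate, under the assumed effects, describes what would happen if the stated count were disregarded; it does not measure a choice that the plan leaves open. Both family sizes would in any case be set to control the false discovery rate at 5% over their own tests.

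Including the barcode is a fair trade-off. In the simulated cases, six tests rather than three raise the chance of a label-pair finding from 52% to 60% if the barcode is rated 1 SD lower, and reduce it from 51% to 44% if it is rated like the text label. Restricting this one outcome to three tests would add an exception to a uniform rule without a clear gain.

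What is left is an editorial mismatch for one single-item secondary outcome. The conclusion rests on reading item 2 of Statistical Methods literally, as applying to every secondary outcome; nothing in the document makes an exception.
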